12.4.2 Statistical model, hypothesis, and method of analysis

The primary objective of the study is to show that at least one SAF312 arm will improve weekly mean pain severity VAS in comparison with its placebo by rejecting the null hypothesis below at a significance level α =0.05 (2-sided).

H1: $u_T=u_v$ vs. H2: $u_T\neq u_v$

where u_T and u_v are mean change from baseline of weekly mean pain severity VAS at Week 12 in SAF312 arm and the placebo arm.

Dunnett procedure will be used to adjust overall type I error (0.05) among the comparisons between each SAF312 arm and the placebo arm.

Mixed model repeated measure (MMRM) analysis will be used with change from baseline at each week on treatment as response variable, and treatment, week, and baseline score as covariates. Two interaction term (treatment*week and baseline*week) will also be included in

the model. An unstructured within subject correlation structure will be used for covariance matrix. The Kenward-Roger approximation will be used to estimate denominator degree of freedom. REML (residual/restricted maximum likelihood) method will be used to estimate parameters.

The two-sided p value for the least square mean (LSM) difference between the SAF312 and the placebo group at each week will be reported for the difference.

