1.2 Purpose

The study is designed to demonstrate the safety and efficacy of two dose concentrations of SAF312 eye drops (5 mg/ml and 15 mg/ml) in subjects with CICP persisting at least for 4 months after refractive or cataract surgery, and chronicity of pain confirmed during the 3 month observation period. The study will also determine the optimal dose to carry forward for further development.

2 Objectives and endpoints

Table 2-1 Objectives and related endpoints

Tak	Table 2-1 Objectives and related endpoints				
Ok	ojective(s)	Endpoint(s)			
Pr	imary objective(s)	ndpoint(s	s) for primary objective(s)		
•	To demonstrate the efficacy of at least 1 of 2 concentrations of SAF312 (5 mg/ml or 15 mg/ml) with superiority to placebo in reducing ocular pain severity		e from baseline to Week 12 in weekly pain severity Visual Analog Scale		
Se	condary objective(s)	indpoint(s	s) for secondary objective(s)		
•	To evaluate additional efficacy of 2 concentrations of SAF312 vs placebo	_	e from baseline to Day 7 and Day 14 ne pain severity VAS		
			e from baseline to Week 12 in pain ncy VAS		
			e from Baseline to Week 12 in Ocular essessment Scale (OPAS) sub-scale of Life		
•	To demonstrate SAF312 does not induce negative effects to the ocular surface after prolonged TRPV1 inhibition	surface conjund	e from baseline to Week 12 in ocular parameters (eg, corneal and ctival staining score, Schirmer score, ctival redness score)		
•	To evaluate the safety of 2 concentrations of SAF312 (0.5 and 1.5%)		rison of adverse events rates n active and placebo		
Ex	ploratory objective(s)	Endpoint(s) for exploratory objective(s)			
•	To monitor a subject's behavior regarding artificial tear/gel/lubricant use		ncy of artificial tear/gel/lubricant use e 12 week treatment period		
•	To monitor a subject's behavior regarding rescue medication use		ncy of rescue medication use over week treatment period		
•	To evaluate corneal nerve density and morphology	corneal	e from Baseline to Week 12 in total nerve fiber length		
		Presen	ce of microneuromas		

Objective(s)	Endpoint(s)	
	Density of corneal dendritiform cells	

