2.2 Secondary Estimands

Not applicable.

3 Study design

Figure 3-1 Study Design

This study is a Phase 2 randomized, double-blinded, multi-center, parallel group, placebo-controlled evaluation of the safety and efficacy of SAF312, 5 mg/ml and 15 mg/ml eye drops versus placebo used twice-daily in both eyes for 12 weeks. Eligible subjects will have undergone refractive surgery (i.e., PRK, LASIK, LASEK, RK, or SMILE) in both eyes or cataract surgery in both eyes, with or without refractive enhancement in one or both eyes at least 4 months prior to Screening, and have been suffering from chronic ocular pain as a result of the their surgery. Both eyes do not necessarily need to have undergone surgery on the same day. If the second eye underwent surgery on a different day than the first, eligibility for time since surgery would be based on the date of the most recent surgery. In cases where more than one procedure was performed on an eye (eg, refractive surgery with CICP followed some time later by cataract surgery, or cataract surgery followed some time later by refractive enhancement), the Screening visit must be \geq 4 months after the most recent procedure. Eligible patients must also demonstrate chronicity of the pain as described in inclusion criteria. Overall approximately 150 subjects will be enrolled in the study (i.e. approximately 50 subjects will be enrolled in each treatment arm in 1:1:1 ratio).

The study will consist of a 12 week observation period starting from Screening Visit (Visit 1) until the Baseline/Randomization Visit (Visit 2). Subjects who qualify for randomization will then be asked to attend visits every two weeks for the first 4 weeks, and then monthly for the remainder of the 12 week treatment period. End of Treatment (EOT) will occur at Visit 6 when the subject receives the last study treatment. End of Study (EOS) will occur 4 days after EOT.

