12.8 Sample size calculation

12.8.1 Primary endpoint(s)

Assuming a true treatment difference in change from baseline in weekly mean pain severity VAS of 15 mm and a SD of 23 mm, a sample size of 50 subjects per arm provides approximately 83% power that the primary analysis will be statistically significant at the two-sided 5% significance level adjusted by 2 comparisons.

See Table 12-1 for power to detect a significant difference from placebo under various assumed treatment effect of weekly mean pain severity VAS and SD.

nQuery Advisor 7.0 is used for the estimate.

Table 12-1 Power to detect a significant difference from placebo under different assumed treatment effects and SD with N = 50 pts/arm

	Treatment effect: difference from placebo in change from baseline in weekly mean pain severity VAS			
SD of change from baseline in weekly mean I pain severity VAS	15	20		
17	98%	>99%		
20	92%	>99%		
23	83%	97%		

The sample size may increase by up to 20% (i.e., 60 pts/arm) in order to maintain power in case dropout increases during the pandemic.

13 Ethical considerations and administrative procedures

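### Name the step-down version of Dunnett, which gives more power for the second dose at the same 5% family-wise error, and label the 83% as one-dose power

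*Protocol*

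**What the plan says.** The test: for the two doses against placebo, Protocol 12.4.2 states "Dunnett procedure will be used to adjust overall type I error (0.05) among the comparisons". SAP 2.5.2 repeats it. Neither document mentions a step-down or closed test. SAP 2.5.2 places the primary inference on the Week 12 difference and reports a two-sided p-value at each week, without saying whether it is adjusted. SAP 2.1 provides for 95% confidence intervals of group differences where appropriate.

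The win criterion: "The primary objective of the study is to show that at least one SAF312 arm will improve weekly mean pain severity VAS", so one dose suffices. A further aim is stated in Protocol 1.2: "The study will also determine the optimal dose to carry forward for further development".

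The power statement (Protocol 12.8.1, repeated in SAP 3) takes 15 mm as the true effect with an SD of 23 mm, and concludes that "a sample size of 50 subjects per arm provides approximately 83% power that the primary analysis will be statistically significant". It describes the level used as "statistically significant at the two-sided 5% significance level adjusted by 2 comparisons". Table 12-1 (SAP Table 3-1) gives one effect and one SD per cell. Neither document says whether one dose or both are assumed to have the effect, and no dropout rate is given.

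**The concern.** Two points arise from the same few sentences.

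1. Single-step Dunnett holds both doses to the same adjusted critical value. Once one dose has been declared effective, only one null hypothesis remains, and testing it at the adjusted value is stricter than 5% family-wise control requires. The two versions can give different verdicts on the second dose from the same data, so the plan should say which applies. The second dose is of interest because the trial also looks for a dose to take forward.

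2. The 83% is attached to the primary analysis, whose objective is at least one of two doses. If the figure is the power for a single dose, it describes a different event from the one it names, and the reader is not told the chance of meeting the objective.

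**Working it through.** **Inputs.** Difference 15 mm, SD 23 mm, 50 per arm, two-sided 5% adjusted for two comparisons (Protocol 12.8.1); 1:1:1 allocation (Protocol section 3); Dunnett at overall 0.05 (Protocol 12.4.2). The model is a three-group comparison at Week 12 with pooled variance. It has no repeated-measures gain, baseline adjustment or missing data, as appears true of the plan's own calculation.

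**Step 1: reproduce the 83%.** The standard error of a difference is 23 × √(2/50) = 4.6 mm, so the noncentrality is 15/4.6 = 3.26. A two-sample t-test on 98 df at two-sided alpha 0.05/2 = 0.025 has power 83.6%. The other cells help to identify the method:

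| SD, effect (mm) | Table 12-1 | One-dose t-test, alpha 0.025 | One dose, Dunnett |
|---|---|---|---|
| 17, 15 | 98% | 98.3% | 98.5% |
| 20, 15 | 92% | 92.8% | 93.4% |
| 23, 15 | 83% | 83.6% | 84.7% |
| 23, 20 | 97% | 97.98% | 98.2% |

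The remaining two cells exceed 99% either way. Cut to whole percents, the alpha 0.025 column matches every cell. The Dunnett column would print 98, 93, 84 and 98. Unadjusted alpha 0.05 gives 89.8% for the 83% cell. The table therefore fits one dose with a Bonferroni split. This is an inference from the figures, since the plan does not name the method.

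**Step 2: critical values.** With equal arms the two contrasts share the placebo arm and have correlation (1/50)/(2/50) = 0.5. Residual df are 3 × 50 − 3 = 147.
- Single-step Dunnett: both |t| values are compared with 2.2335 (nominal p 0.0270).
- Step-down Dunnett: the larger |t| is compared with 2.2335. If it exceeds that, the other is compared with the ordinary t value, 1.976.

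This is a closed test: the joint null is tested by Dunnett at 5%, and each single null by a t-test at 5%. It rejects whatever single-step rejects. At a pooled SD of exactly 23, the second dose must show 2.2335 × 4.6 = 10.3 mm under single-step and 1.976 × 4.6 = 9.1 mm under step-down. A second dose between those values gets opposite verdicts.

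**Step 3: power, 50 evaluable per arm, SD 23** (simulation, 2 million trials per scenario in the main runs).

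| True effects (mm) | Event | Single-step | Step-down |
|---|---|---|---|
| 15 and 15 | each dose | 84.7% | 88.3% |
| | both doses | 75.4% | 82.7% |
| | at least one | 94.0% | 94.0% |
| 15 and 10 | weaker dose | 47.8% | 56.6% |
| | both doses | 45.1% | 55.1% |
| 15 and 7.5 | weaker dose | 27.6% | 36.1% |
| | at least one | 85.6% | 85.6% |
| 15 and 0 | at least one | 85.5% | 85.5% |

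Consistency check, 15 and 15 mm, single-step: 84.7 + 84.7 − 75.4 = 94.0.

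**Step 4: error under step-down.** The error rate is 5.0% with both doses null, 4.4% for a null dose beside a 15 mm dose, and 5.0% for a null dose beside a very effective one.

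**Step 5: fewer or more evaluable subjects.** The plan gives no dropout rate, so the numbers per arm are assumptions, except that 60 is the plan's own optional maximum.

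| Evaluable per arm | One dose, alpha 0.025 | At least one (15 and 15) | At least one (15 and 0) | Both doses (15 and 15): single-step / step-down |
|---|---|---|---|---|
| 40 | 73.5% | 87.9% | 76.1% | 62.2% / 71.4% |
| 45 | 79.0% | 91.4% | 81.2% | 69.2% / 77.6% |
| 50 | 83.6% | 94.0% | 85.5% | 75.4% / 82.7% |
| 60 | 90.2% | 97.1% | 91.5% | 84.7% / 90.0% |

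**The case against.** The plan contains no error here. It controls the family-wise error with a recognised, pre-specified method, and its success criterion needs only one dose, for which step-down adds nothing. Choosing between two valid procedures could be called preference. This stands as a limit on the weight of the point: the gain is for the second dose only. Single-step is also an inference, since the text says only Dunnett; if step-down was meant, the wording still needs to say so.

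A reader might infer that single-step testing distorts the choice of dose. The documents do not support that. No section ties the choice to significance of both doses, and no dose-against-dose test is planned. The difference from placebo is reported for each dose under either version.

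A reader might also infer that step-down has no cost because SAP 2.5.2 speaks only of p-values. That is not safe either. SAP 2.5.2 does not call those p-values adjusted, and SAP 2.1 leaves room for 95% intervals of group differences. An ordinary or single-step simultaneous interval may disagree with the step-down decision on the second dose.

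On the power label, the table title, the single effect per cell and the wording about two comparisons already point to power per comparison. That is fair, but the sentence still attaches the figure to the primary analysis.

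**Conclusion.** The point holds as one of efficiency and labelling, not validity. At the same 5% family-wise error, step-down Dunnett raises both-dose power by 82.7 − 75.4 = 7.3 points when both doses give 15 mm, and weaker-dose power by 56.6 − 47.8 = 8.8 points when they give 15 and 10 mm. At-least-one power is unchanged.

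The 83% fits one dose at two-sided alpha 0.025. For the stated objective under planned Dunnett, power is 94.0% if both doses give 15 mm and 85.5% if only one does. The large gap from 83% therefore needs both doses to work, a pattern the documents do not state.

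It would be wrong to read the label as a sign of an underpowered trial. With 50 evaluable per arm, 83% is conservative for the objective, and no sample-size change follows. The at-least-one figures do depend on 50 evaluable per arm. The primary estimand sets aside data from rescue days and after treatment discontinuation (Protocol 12.4.3), so fewer may contribute. With 45 evaluable and only one effective dose, power is 81.2%.

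**What to change.** 1. In Protocol 12.4.2 and SAP 2.5.2, before unblinding, name the step-down Dunnett procedure at Week 12, and give the rule: the larger statistic against the Dunnett value and, only if it rejects, the other against the unadjusted two-sided 5% value. If only the SAP is changed, record it in SAP section 4, which now lists no changes.

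2. In the same place, state which confidence intervals will accompany the two Week 12 contrasts, and note that ordinary or single-step simultaneous 95% intervals may not match the step-down decision for the second dose.

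3. In Protocol 12.8.1 and SAP 3, label 83% and the table as power for one dose against placebo at two-sided alpha 0.025. Add the at-least-one power under Dunnett: about 94% if both doses give 15 mm and about 85% if only one does. Say that both assume 50 evaluable per arm, are lower with dropout, and that no dropout rate has been assumed.

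Cost: a few words on the method, a small code change and two sentences on power. The one real downside is the interval mismatch in item 2. Family-wise error, sample size and trial conduct are unaffected.

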12.4.3 Handling of intercurrent events of primary estimand

In the primary analysis, the estimand will be the treatment effect of SAF312 against placebo, had subjects not taken prohibited or rescue medications as described below, and had they stayed on the study treatment for the whole study duration. The hypothetical strategy assumes the subjects with Intercurrent events (IEs) will behave like other subjects who did not take rescue/prohibited medications and stayed on study treatment.

For subjects who use rescue medications for pain relief due to any reason, the data on the day(s) will be excluded and treated as missing.

For subjects who take the following prohibited medications:

- Ocular, nasal, inhaled, or systemic corticosteroids
- Use of oral or topical ocular antihistamines, mast cell stabilizers

The data on the day(s) + 3 days following the last day of these prohibited medications will be excluded and treated as missing.

For subjects with new use or changes in dosing of neuromodulators for any reason or topical ocular NGF, the data starting from the day will be excluded and treated as missing.

For subjects who discontinue study treatment for any reason, the data collected following the treatment discontinuation will be excluded and treated as missing. Missing data after study treatment discontinuation will be based on the Missing at Random (MAR) assumption.

The multiple imputations will be carried out on the weekly mean pain severity VAS.

12.4.4 Handling of missing values not related to intercurrent event

The primary MMRM model implicitly imputes missing data under a MAR assumption.

Handling of missing daily pain severity values within a week (within-week imputation)

The weekly mean of the seven 24-hour average pain severity assessments will be calculated based on the available assessments. If only one measurement is available, the mean will be based on that value.

Handling of missing weekly mean pain score values (weekly mean imputation)

For all analyses, imputation of intermittent missing observations before treatment discontinuation will be carried out following a MAR mechanism for all treatment arms.

12.4.5 Sensitivity analyses for primary endpoint/estimand

Not applicable.

12.4.6 Supplementary analysis

A supplementary clinical question of interest is: What is the effect of SAF312 versus placebo on change from baseline in weekly mean pain severity VAS score, regardless of discontinuation from study treatment discontinuations for any reason, and regardless of occasional use of rescue medication or prohibited medications?

The supplementary analysis to the primary analysis will be performed on the FAS population. The supplementary analysis will be performed using all observed data regardless of intercurrent events (a treatment policy strategy). The target population, the primary variable and the summary measure of the supplementary estimand for the supplementary estimand are the same as for the primary estimand. Differently from the primary estimand, this analysis considers all intercurrent events are inherent in the treatment regimen and will not exclude any observed data even when subjects take rescue/prohibited medications or discontinue treatment.

For subjects who use rescue medications for pain relief due to any reason, all observed data will be used for analysis. If not available, missing data will be under the MAR assumption for both SAF312 and placebo arms.

For subjects who take the following prohibited medications:

- Ocular, nasal, inhaled, or systemic corticosteroids
- Use of oral or topical ocular antihistamines, mast cell stabilizers

All observed data will be used for analysis. If not available, missing data on the day(s) +3 days of the IEs will be under the MAR assumption for both SAF312 arms and placebo arm.

For subjects with new use or change in dosing of neuromodulators for any reason or topical ocular NGF, all observed data will be used for analysis. If not available, missing data on the days of IEs will be under the MAR assumption for both SAF312 and placebo arms.

For subjects who discontinue from study treatment due to any reason, retrieved drop-out (RDO) data collected after study treatment discontinuation will be used for analysis. If not available, missing data after treatment discontinuation will be multiply imputed based on Jump to Reference assumption for SAF312 arms and under the MAR assumption for placebo arm.

The supplementary analysis will be performed using MMRM but includes all the observed data and imputed data if appropriate.

Subgroup analysis

Subgroup analyses of the primary endpoints will be outlined in the statistical analysis plan (SAP).

12.5 Analysis supporting secondary objectives

For secondary endpoints:

- Change from baseline in pain severity Visual Analog Scale (VAS) at Day 7 and Day 14
- Change from baseline to Week 12 in pain frequency VAS

- Protocol No. CSAF312B12201
- Change from baseline in OPAS subscale Quality of Life at Week 12
- Change from baseline to Week 12 in ocular surface parameters (corneal staining score, conjunctival staining score, Schirmer score, conjunctival redness score)

Summary statistics (mean, median, 25th percentile, 75th percentile, standard deviation, minimum and maximum, the number of non-missing observations, and 95% confidence interval) by treatment arm will be provided. 95% confidence interval will be provided for the difference between the SAF312 arm vs. placebo for pain severity VAS, pain frequency VAS, and OPAS subscale Quality of Life.

12.5.1 Safety endpoints

For all safety analyses, the safety set will be used. The safety assessments are adverse events (ocular and non-ocular), slit lamp biomicroscopy, IOP, visual acuity, ophthalmoscopy, and corneal endothelial cells evaluations. All listings and tables will be presented by treatment group.

Safety summaries (tables, figures) include only data from the on-treatment period with the exception of baseline data which will also be summarized where appropriate (e.g. change from baseline summaries). In addition, a separate summary for death including on treatment and post treatment deaths will be provided. In particular, summary tables for adverse events (AEs) will summarize only on-treatment events, with a start date during the on-treatment period (treatment-emergent AEs).

The on-treatment period starts from the date of the first administration of study treatment to 4 days after the date of the last administration of study treatment.

The safety analysis will consist of descriptive summaries. Continuous variables will be presented with n, mean, SD, median, minimum and maximum. Categorical data will be displayed with frequency and percentage.

Adverse events

All information obtained on adverse events will be displayed by treatment group and subject.

The number (and percentage) of subjects with treatment emergent adverse events (events started after the first dose of study medication or events present prior to start of double-blind treatment but increased in severity based on preferred term) will be summarized in the following ways:

- by treatment, primary system organ class and preferred term.
- by treatment, primary system organ class, preferred term and maximum severity.
- by treatment, Standardized MedDRA Query (SMQ) and preferred term.

Ocular and non-ocular adverse events will be summarized separately. Separate summaries will be provided for study treatment related adverse events, death, SAE, other significant adverse events leading to discontinuation.

Subject listings of all adverse events will be provided. Deaths and other serious or clinically significant non-fatal adverse events will be listed separately. A subject with multiple adverse events within a primary system organ class is only counted once towards the total of the primary system organ class.

12.5.2 Patient reported outcomes

Patient-reported outcomes include the following:

• OPAS questionnaire subscales

Summary of change from baseline will be provided by treatment group. No test will be performed on the PRO endpoints.

12.6 Analysis of exploratory endpoints

Exploratory endpoints include:

- Frequency of artificial tears/gel/lubricant use over the 12-week treatment period
- Frequency of rescue medication use over the 12-week treatment period
- Change from Baseline to Week 12 in total corneal nerve fiber length
- Presence of microneuromas
- Density of corneal dendritiform cells

The analysis will be based on FAS.

For continuous endpoints, summary statistics (mean, median, 25th percentile, 75th percentile, SD, minimum and maximum, the number of non-missing observations, and 95% confidence interval) will be provided by treatment arm at each time point. Differences of change from baseline endpoints between each SAF312 arm vs. placebo will be summarized at each post-baseline visit with 95% confidence interval.

For frequency of pain events, artificial tears/gel/lubricant, rescue medications, and microneuromas, percentage of subjects by treatment group over time will be presented. The difference in percentage between each SAF312 and placebo will be summarized with 95% confidence interval.

